4.5 Other Events Requiring Immediate Reporting

The following events must be reported ***within 24 hours*** by fax to MedImmune Patient Safety using the fax notification form:

- 1) Any withdrawal of consent during the study
- 2) Pregnancy or intent to become pregnant*

* Subjects who become pregnant during the study period must not receive additional doses of investigational product but will be followed for the duration of the study. A pregnancy should be followed for outcome, any premature terminations reported, and the health status of the mother and child, including date of delivery and the child's gender and weight, should be reported to MedImmune Patient Safety after delivery.

4.6 Safety Management During the Study

The MedImmune medical monitor has primary responsibility for the ongoing medical review of safety data throughout the study. This includes immediate review of SAEs and timely review of other AEs reported during the study. The MedImmune Patient Safety Specialist has responsibility for the day-to-day safety monitoring of the study, including the receipt, review, investigation, and follow-up of SAEs reported by the clinical study sites.

The MedImmune Safety Monitoring Committee (SMC) will independently review cumulative safety surveillance data, as well as the decisions of the Medical Monitor regarding dose escalation, on a regular basis throughout the study and make recommendations regarding further conduct of the study. The MedImmune SMC will also review safety data at other timepoints in response to AEs felt to be medically significant by the medical monitor. The MedImmune SMC is composed of at least 2 MedImmune physicians who are not directly involved in the day to day operations of the study, and at least 2 physicians who are not employees of MedImmune.

4.7 Interruption or Discontinuation of Study Dosing in Individual Subjects

An individual subject will not receive any further investigational product if any of the following occur in the subject in question:

- 1) Withdrawal of consent
- 2) Grade 2 or greater allergic reactions. Grade ≤ 3 infusion reactions that respond to medical therapy or slowing the infusion rate and are of limited duration will not necessitate dose interruption or discontinuation. Any infusion or allergic reaction that necessitates the use of systemic pressor agents will cause dose discontinuation in that subject.
- 3) Pregnancy or intent to become pregnant
- 4) DLT (see Section 4.10 for definition of DLTs, dose escalation phase only).
- 5) Occurrence of Grade 3 or Grade 4 hematologic or non-hematologic toxicity after the first cycle of treatment
- 6) Grade ≥ 2 toxicities (after completion of Cycle 1) that do not return to Grade ≤ 1 or baseline within 7 days unless clearly attributable to other causes such as disease progression or accident.
- 7) Grade ≥ 2 toxicities that cause a cumulative delay of ≥ 21 days in 3 consecutive cycles (Cohorts 1 through 5 and the expansion phase)
- 8) Documentation of disease progression

- 9) Event which in the opinion of the investigator contraindicates further dosing such as intercurrent illnesses, significant drug toxicities or complications if judged by the investigator to be in the best interest of the subject
- 10) Subject non-compliance
- 11) Treatment with another investigational agent
- 12) Initiation of alternative anticancer therapy

Subjects who are permanently discontinued from investigational product will be followed for the full study period (through 30 days after the last dose of MEDI-573), including the collection of any protocol-specified blood and urine specimens, unless consent is withdrawn.

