3.5.5 Dose Modifications of MEDI-573 Due to Toxicity

Dose modifications of MEDI-573 will be based on hematologic and nonhematologic toxicities that cannot be attributed to another cause such as disease progression or accident following the first cycle of treatment ([Table 3.5.5-1](#)). Both hematologic and nonhematologic toxicities will be graded according to NCI CTCAE V3.0. All DLTs must be documented as an AE on the source document.

Table 3.5.5-1 MEDI-573 Dose Modification Table

Hematologic or Nonhematologic Toxicity	Dose Modification of MEDI-573
Grade ≤ 1	None
Grade 2	
Cohorts 1 through 5 and the Expansion Phase
 
Withhold MEDI-573 for up to 7 days until resolution to Grade ≤ 1 or baseline and resume at current dose level. Grade 2 laboratory toxicities that do not have clinical significance may not require dose delay. The Medical Monitor should be consulted in the event of Grade 2 laboratory toxicities that are deemed clinically insignificant to determine if dosing may continue.
 
Discontinue MEDI-573 if MEDI-573 is withheld for > 7 days without resolution of toxicity to Grade ≤ 1 or baseline unless clearly attributable to another cause such as disease progression or accident.
 
Cohorts 6 and 7 (if applicable)
 
The Medical Monitor should be consulted in the event of Grade 2 laboratory toxicities that are deemed clinically insignificant to determine if dosing may continue.
 
Discontinue MEDI-573 if the toxicity does not return to Grade ≤ 1 or baseline prior to Day 1 of the subsequent cycle unless clearly attributable to another cause such as disease progression or accident.

Table 3.5.5-1 MEDI-573 Dose Modification Table

Hematologic or Nonhematologic Toxicity	Dose Modification of MEDI-573

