Grade 3 or 4	
First Occurrence:
 
Cohorts 1 through 5 and the Expansion Phase: Withhold MEDI-573 for up to 7 days until resolution to Grade ≤ 1 or baseline. Discontinue MEDI-573 if no clinical benefit has been documented . If MEDI-573 is withheld for > 7 days without resolution of toxicity to Grade ≤ 1 or baseline, discontinue MEDI-573 regardless of clinical benefit
 
Cohorts 6 and 7 (if applicable) Discontinue MEDI-573 if no clinical benefit has been documented and the toxicity does not resolve to Grade ≤1 or baseline by Day 1 of the subsequent cycle.
 
For all subjects who experience a Grade 3 or 4 toxicity that resolves as above, and who have achieved some degree of clinical benefit while on MEDI-573 therapy, the Food and Drug Administration (FDA) will be consulted regarding the possibility of continued administration of MEDI-573. MEDI-573 therapy should not be continued without agreement from the FDA.
 
Second Occurrence: Discontinue MEDI-573.

If Grade ≥ 3 toxicity that is at least possibly attributable to MEDI-573 is observed in a subject in the second or greater cycle, dose escalation will be temporarily suspended to review the cumulative safety data. Such an event may prompt cessation of dose escalation or modification of the dose-escalation scheme, including lowering of subsequent doses from the first cycle dose, if appropriate. Subjects may continue to receive MEDI-573 during this review and subjects may continue to be enrolled into an open cohort until a determination of necessary action, if any, is made.

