4.10 Definitions of Dose-limiting Toxicities

Dose-limiting toxicities will be graded according to the NCI CTCAE V3.0 and will be assessed during the first cycle of treatment with MEDI-573 (Cycle 1, Day 1 through Cycle 1, Day 21).

A DLT is defined as:

- 1) Any Grade 3 or higher non-hematologic toxicity that occurs during the DLT assessment period where a cause other than the investigational product (such as disease progression or accident) cannot be reasonably justified with the following exceptions:
 - Grade < 4 serum-high glucose (fasting) with duration of < 24 hours.
 - Grade 3 fever (in the absence of neutropenia) defined as > 40.0°C (>104.0°F) that resolves to normal or baseline within 24 hours of treatment and is not considered an SAE; or
 - Grade 3 rigors/chills that respond to optimal therapy.
- 2) Any Grade 3 or higher hematologic toxicity that occurs during the DLT assessment period where a cause other than the investigational product (such as disease progression or accident) cannot be reasonably justified.

5 Statistical Considerations

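### Section 4.7 item 2 lets a subject continue after a responsive, brief Grade 3 infusion reaction, while items 4 and 5 of the same list end dosing for that event

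*Protocol*

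**What the plan says.** Section 4.7 opens by stopping all further product if any one item on its list occurs. Four provisions bear on a Grade 3 infusion reaction that responds to treatment, is short, and needs no pressors.

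- **4.7 item 2** first makes allergic reactions of Grade 2 or above a reason to stop. It then says that "Grade ≤ 3 infusion reactions that respond to medical therapy or slowing the infusion rate and are of limited duration will not necessitate dose interruption", and the sentence adds discontinuation. No cycle or phase is named.
- **4.7 item 4** stops dosing for a "DLT (see Section 4.10 for definition of DLTs, dose escalation phase only". Section 4.10 counts as a DLT "Any Grade 3 or higher non-hematologic toxicity that occurs during the DLT assessment period" (Cycle 1, Days 1 to 21) unless another cause can reasonably be justified. The only exceptions are short-lived high glucose, short-lived Grade 3 fever and Grade 3 rigors or chills that respond.
- **4.7 item 5** stops dosing on "Occurrence of Grade 3 or Grade 4 hematologic or non-hematologic toxicity after the first cycle of treatment". It has no phase limit and no exceptions.
- **Section 3.5.5 and Table 3.5.5-1** deal with "toxicities that cannot be attributed to another cause such as disease progression or accident following the first cycle of treatment". At a first Grade 3 or 4 event, Cohorts 1 to 5 and expansion are told "Withhold MEDI-573 for up to 7 days until resolution to Grade ≤ 1 or baseline. Discontinue MEDI-573 if no clinical benefit has been documented". Cohorts 6 and 7 are told "Discontinue MEDI-573 if no clinical benefit has been documented and the toxicity does not resolve to Grade" 1 or below, or baseline, by the next Day 1. If the toxicity resolves and there is clinical benefit, the FDA is consulted, and "MEDI-573 therapy should not be continued without agreement from the FDA".

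Section 3.5.4 item 3 describes how to manage an infusion reaction: slow the infusion or pause it for up to 4 hours, and restart at half rate. It adds methylprednisolone for severe or prolonged reactions, and the next sentence says prophylaxis may be considered at later doses.

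**The concern.** These rules decide whether one patient is infused again, and for one foreseeable event they point in opposite directions. A site that follows item 2, and reads Section 3.5.4 in its light, could re-infuse a subject whom item 4 or 5 withdraws. A site that follows item 4 or 5 would withdraw a subject whom item 2 appears to keep on treatment. Part of the decision falls during the visit, because Section 3.5.4 lets a paused infusion be restarted the same day. The stakes are individual safety and consistent treatment. The 3+3 count under Section 4.9 is not at stake, since it depends on Section 4.10 and not on item 2.

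**Working it through.** **Rule trace.** There is no planned figure to reproduce, so the check follows one event (Grade 3, responsive, brief, no pressors) through each rule.

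| Situation | 4.7 item 2 | 4.7 items 4 and 5 | Table 3.5.5-1 | Result |
|---|---|---|---|---|
| Cycle 1, escalation | continue | DLT, so item 4 stops dosing, unless it is only the excepted fever or rigors/chills | not in force | conflict |
| Cycle 1, expansion | continue | neither applies | not in force | no conflict |
| After Cycle 1, Cohorts 1–5 and expansion | continue, no interruption | item 5 stops dosing | withhold; stop if no benefit; with benefit, FDA agreement | conflict, three answers |
| After Cycle 1, Cohorts 6–7 | continue | item 5 stops dosing | stop only if no benefit and unresolved by next Day 1; with benefit, FDA agreement | conflict |

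The other-cause clause in Section 4.10 will seldom help, because an infusion reaction is ordinarily due to the product. The last two rows also show that item 5 and the table disagree with each other even if item 2 is ignored.

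**Subjects exposed.** Assuming Cohorts 1 to 5 are complete (17 treated, Section 1.5), the subjects still to be treated are:
- Item 2 against item 4: 3 in Cohort 6, and 3 more if Cohort 7 opens. Under Section 4.9 a cohort grows to 6 only after a DLT.
- Item 2 against item 5: those 3 to 6, plus about 10 expansion subjects, or 20 if the lower-dose cohort opens, as far as they reach Cycle 2.

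**Chance of at least one event.** The Protocol gives no rate, so p = 1% to 5% per subject is an assumption. The formula is 1 − (1 − p)^n.
- n = 3: 1 − 0.99^3 = 0.030; 1 − 0.95^3 = 0.143.
- n = 6: 1 − 0.99^6 = 0.059; 1 − 0.95^6 = 0.265.
- n = 10 (first expansion cohort, same p after Cycle 1, all reaching Cycle 2): 1 − 0.99^10 = 0.096; 1 − 0.95^10 = 0.401. Taking all 10 as at risk is an upper bound.

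**Is the assumed range compatible with the data?** Section 1.5 reports no related AE above Grade 2 in 17 subjects. The one-sided 95% upper limit for 0 of 17 is 1 − 0.05^(1/17) = 0.16, so 1% to 5% is not excluded.

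**Does earlier tolerance carry over?** Only partly. The highest weekly dose was 15 mg/kg over 60 minutes: 15/60 = 0.25 mg/kg/min. Appendix 4 gives Cohorts 6 and 7 as 30 and 45 mg/kg over 90 minutes: 30/90 = 0.33 and 45/90 = 0.50 mg/kg/min.

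**The case against.** The best defence is the structure of Section 4.7. Each listed event is sufficient alone, so items 4 and 5 apply whatever item 2 says. On this reading the infusion-reaction sentence only separates such reactions from the allergic-reaction trigger beside it: item 2 itself does not require stopping. This is the better reading, and it softens the conflict. It does not remove it. It would leave the express Grade 3 allowance with effect only in Cycle 1 of expansion and, in Cycle 1 of escalation, for reactions confined to the excepted fever or rigors/chills. A site could fairly take item 2 as the specific rule for infusion reactions, and no text states precedence.

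Several narrower points stand:
- Section 3.5.4 covers reactions of every grade, and its prophylaxis sentence does not by itself authorise re-dosing after Grade 3. It adds doubt but is not a separate contradiction.
- How often a brief, responsive reaction is graded 3 depends on CTCAE V3.0, which the Protocol only links to.
- The rates are assumed, and carrying the Cycle 1 rate into later cycles has no support in the data.
- The 10-subject figure covers only the first expansion cohort, not everyone at risk after Cycle 1.
- In Cohorts 6 and 7 the next dose is at least 21 days away, which allows medical review. Pressor use, investigator judgment and the study halt for anaphylaxis also limit harm. None of these says which rule governs this event, and the 21 days do not cover a same-day restart.
- The disagreement between item 5 and the table is a separate matter, though any repair has to settle it.

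**Conclusion.** The contradiction is real and should be fixed. For a responsive, brief Grade 3 infusion reaction, item 2 conflicts with item 4 in Cycle 1 of escalation and with item 5 after Cycle 1 in all phases; the two sides agree only in Cycle 1 of expansion. The event is probably rare. Under the assumed 1% to 5% per subject, the chance of at least one Cycle 1 case is 3% to 14% with Cohort 6 alone and 6% to 26% with Cohorts 6 and 7. After Cycle 1 it is at most 10% to 40% in the first 10 expansion subjects. These figures show scale only. The conflict rests on the text and does not depend on them. The effect is confined to individual subjects; DLT counting and the MTD rule are untouched.

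**What to change.** Before Cohort 6 is dosed:

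1. Add to Section 4.7 item 2: *unless the event is a DLT under Section 4.10 (item 4) or a Grade 3 toxicity after Cycle 1 (item 5)*.
2. Make the prophylaxis sentence in Section 3.5.4 item 3 subject to Section 4.7.
3. State whether item 5 or the FDA-agreement route in Table 3.5.5-1 governs after Cycle 1.

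If the sponsor does intend re-dosing, the alternative is to except responsive Grade 3 infusion reactions of limited duration in Section 4.10, in item 5 and in the Grade 3 or 4 row of the table. The choice is a clinical one for the sponsor.

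Either route costs a few words of amendment text. The first changes nothing in design, sample size or analysis; the alternative also changes the DLT definition.

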In the dose escalation phase (Cohorts 1 through 5 only) and the dose expansion phase, in Cycle 2 and beyond, a dose can be delayed up to 7 days based on hematologic and nonhematologic toxicities, according to the conditions described in Section 3.5.5, but all 3 doses (Cohorts 1 through 5 and the dose expansion phase) must be completed within the cycle in order for the cycle to be considered complete. Subjects who do not receive all required doses within a cycle will not advance to the next cycle and will be removed from treatment. Each new cycle will begin 7 days after the last dose of the previous cycle (Cohorts 1 through 5 and the dose expansion phase). Subjects in Cohorts 6 and 7 cannot have a delay in treatment due to hematologic or nonhematologic toxicities. For Cohorts 1 through 5 and the expansion phase, all visits during Cycle 2 and subsequent visits may occur in a ± 2 -day window to accommodate schedule changes, but doses of MEDI-573 must not occur more frequently than every 6 days. For Cohorts 6 and 7 (if applicable), all visits during Cycle 2 and subsequent visits may occur in a + 2-day window to accommodate schedule changes, but dosing of MEDI-573 must not occur more frequently than every 21 days.

Treatment with MEDI-573 will continue until unacceptable toxicity, documentation of disease progression, or other reasons for subject withdrawal. Rules for dose-escalation are described in Section 4.9. Intra-subject dose-escalation will not be allowed. Dose reduction for toxicities other than DLTs will be allowed as described in Section 3.5.5.

Table 3.5.2-1 Summary of Dose Cohorts

Dose Cohort	Number of Subjects	MEDI-573 Dose
1	3-6	[REDACTED] IV infusion once every 7 days
2	3-6	[REDACTED] infusion once every 7 days

Table 3.5.2-1 Summary of Dose Cohorts

Dose Cohort	Number of Subjects	MEDI-573 Dose
3	3-6	██████████ IV infusion once every 7 days
4	3-6	██████████ IV infusion once every 7 days
5	3-6	██████████ IV infusion once every 7 days
6	3-6	██████████ V infusion once every 21 days
7 (if applicable)	3-6	██████████ IV infusion once every 21 days
Dose-expansion	Up to 20	██████████ IV infusion once every 7 days

IV = intravenous

Note: The dose-expansion phase will evaluate PK and pharmacodynamic parameters and determine tumor response in approximately 20 subjects with advanced urothelial carcinoma (eg, bladder cancer).

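### In Cycle 1 of the expansion phase, no graded stop or hold covers a toxicity that meets the DLT criteria before the Day 15 dose (allergic and infusion reactions aside)

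*Protocol*

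**What the plan says.** All references are to the Protocol.

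- **4.7 item 4** stops dosing in an individual subject for "DLT (see Section 4.10 for definition of DLTs, dose escalation phase only").
- **4.7 item 5** stops dosing for "Occurrence of Grade 3 or Grade 4 hematologic or non-hematologic toxicity after the first cycle of treatment". Item 6 (Grade 2 or higher toxicity not resolved within 7 days) likewise applies only once Cycle 1 is complete.
- **4.7 item 2** covers "Grade 2 or greater allergic reactions" and sets conditions for infusion reactions, in any cycle and either phase.
- **4.7 item 9** stops dosing for an "Event which in the opinion of the investigator contraindicates further dosing such as intercurrent illnesses, significant drug toxicities or complications", with no grade attached.
- **3.5.5 and Table 3.5.5-1** name the expansion phase, but the section covers toxicities that cannot be put down to "another cause such as disease progression or accident following the first cycle of treatment". Its separate review trigger is a Grade 3 or higher, possibly related toxicity "in the second or greater cycle, dose escalation will be temporarily suspended to review the cumulative safety data".
- **3.5.2** says that in "Cycle 2 and beyond, a dose can be delayed up to 7 days based on hematologic and nonhematologic toxicities". It also says: "Subjects who do not receive all required doses within a cycle will not advance to the next cycle and will be removed from treatment".
- **4.10** defines a DLT over Cycle 1, Days 1 to 21, as Grade 3 or higher toxicity without another reasonable cause. The exceptions are short-lived high glucose below Grade 4, certain Grade 3 fever, and Grade 3 rigors or chills that respond to therapy.
- **2.4** schedules expansion doses on Days 1, 8 and 15 of each 21-day cycle.

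**The concern.** Item 4 is the only graded individual stop that works in Cycle 1 apart from the allergic and infusion reaction rule, and it is closed to expansion subjects. Keeping expansion events out of the 3+3 count is sensible. Because the limit was placed in the individual stopping rule, however, it also removes the subject's own protection.

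The stake is patient safety in a first-in-human study. An expansion subject has a weaker written rule at first exposure than from Cycle 2 on, and a weaker one than an escalation subject with the same DLT. The first 10 expansion subjects receive the higher of the two expansion doses.

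**Working it through.** No figure in the plan needs reproducing. The check reads each rule by phase and cycle for one defined event: a toxicity that meets 4.10 and is not an allergic or infusion reaction under 4.7 item 2.

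| Rule | Escalation, Cycle 1 | Expansion, Cycle 1 | Expansion, Cycle 2 on |
|---|---|---|---|
| 4.7 item 4 (DLT) | mandatory stop | excluded by its wording | not applicable |
| 4.7 item 5 (Grade 3 or 4) | not yet in force | not yet in force | mandatory stop |
| 4.7 item 6 (Grade 2 or higher, unresolved) | not yet in force | not yet in force | mandatory stop |
| Table 3.5.5-1 | not yet in force | not yet in force | mandatory hold or stop |
| 3.5.2 toxicity delay | not provided | not provided | up to 7 days |
| 4.7 item 9 | judgment | judgment | judgment |
| 4.8 item 3 (whole study) | judgment | judgment | judgment |

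4.7 item 7 adds nothing in Cycle 1, because it counts toxicity delays and 3.5.2 provides for these only from Cycle 2. Items 1 and 2 of 4.8 cover related death and anaphylaxis only. From Cycle 2, item 5 and the table differ in strictness: the table allows continuation after resolution, with clinical benefit and FDA agreement. Both still bind by grade.

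**Doses at issue.** Cycle 1 has 3 doses (Days 1, 8, 15). Doses remaining = 3 minus doses already given:

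- event after the Day 1 dose and before Day 8: 3 − 1 = 2
- event after the Day 8 dose and before Day 15: 3 − 2 = 1
- event after the Day 15 dose: 3 − 3 = 0

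A weekly-schedule escalation subject with the same DLT receives 0 further doses in each case.

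**What the text leaves.** With no toxicity delay in Cycle 1 and removal for an incomplete cycle, the written choice is to dose on schedule or to end treatment. No grade is given for making that choice.

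**The case against.** The strongest reply is that the limit is deliberate and the remaining protection is real. Appendix 4 records that the DLT period was meant to apply only to escalation subjects. Both expansion doses had already been explored, with no DLT in 17 subjects and treatment-related events of Grade 1 or 2 only (1.5, 2.4). Item 9 binds once the investigator judges that dosing is contraindicated, and it names significant drug toxicities. Treatment also ends at unacceptable toxicity. Under 4.6 the medical monitor reviews SAEs immediately and the safety committee meets regularly and ad hoc. Under 4.8 item 3 the monitor can halt dosing across the study. A Cycle 1 dose withheld and not given already leads to removal.

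Most of this stands, and it limits the weight of the point. It does not answer it: none of these safeguards fixes by grade whether the affected subject gets the next dose. The wish to keep expansion events out of the DLT assessment is no reason to drop the individual stop.

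A reader might infer more than the text supports:

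- **That every Grade 3 or 4 event in Cycle 1 would stop an escalation subject.** It would not. Events exempted by 4.10 have no graded Cycle 1 stop in either phase and lie outside this point.
- **That the exposure gap covers all of Days 1 to 21.** No Cycle 1 dose remains after Day 15, and a toxicity that persists can come under item 6 or Table 3.5.5-1 before Cycle 2 starts.
- **That the 17 treated subjects give a usable event rate.** They pool dose levels and all follow-up to the cutoff, not Cycle 1 at the expansion doses.

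**Conclusion.** The point holds in this form and should be fixed. For an expansion subject whose Cycle 1 toxicity meets 4.10 before the Day 15 dose, and is not an item 2 reaction, the Protocol has no graded mandatory stop or hold. Up to 2 of 3 Cycle 1 doses then depend on ungraded judgment. How often this would happen cannot be estimated from the document and may be rare.

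The conclusion assumes that the opening sentence of 3.5.5 limits Table 3.5.5-1 to toxicities after Cycle 1. Section 3.5.2, with delays only from Cycle 2, supports that reading.

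It would go too far to say that expansion subjects are unprotected or must be dosed through toxicity, since item 9 can stop them. MTD determination is also untouched, because the 3+3 rules in 4.9 concern escalation cohorts.

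**What to change.** In 4.7 item 4, replace the restriction to the escalation phase with:

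> In the expansion phase, a Cycle 1 event meeting the Section 4.10 criteria also stops dosing in that subject; it is not counted in the Section 4.9 3+3 decisions.

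This keeps the purpose of the existing limit and restores the individual stop. As worded it covers all of Cycle 1, so it also stops a subject whose event follows the Day 15 dose, as item 4 already does in escalation.

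The cost is one sentence, with no added subjects or procedures. The downside is that a few expansion subjects may stop who could have continued at the investigator's discretion, and they may lack the biopsy due between the last Cycle 1 dose and Cycle 2. That tissue feeds the decision on the lower-dose expansion cohort (4.9). The documents give no rate for this loss. Part of it exists already, because a subject whose Cycle 1 dose is withheld and not given is removed under 3.5.2.

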MEDI-573 will be administered once every 7 days (on Days 1, 8, and 15 of each 21-day treatment cycle) as [REDACTED] intravenous (IV) infusion (Cohorts 1 through 5 and the expansion phase) or once every 21 days (on Day 1 of each 21-day treatment cycle) as [REDACTED] infusion (Cohorts 6 and 7). Treatment will continue until unacceptable toxicity, documentation of disease progression, or other reasons for subject withdrawal. Intra-subject dose-escalation will not be allowed. Dose reduction for toxicities other than DLTs will be allowed as described in Section 3.5.5. Rules for interruption or discontinuation of MEDI-573 in individual subjects are described in Section 4.7. Rules for interruption or discontinuation of MEDI-573 and study entry are described in Section 4.8.

Dose escalation will follow a standard 3+3 study design. Rules for dose escalation and dose expansion are described in Section 4.9.

The first 10 subjects enrolled into the dose-expansion phase will receive doses of MEDI-573 [REDACTED] every 7 days. The decision to continue enrollment in the lower [REDACTED] dose-expansion cohort will be based on pharmacodynamic assessments of tissue obtained from subjects pre- and post-exposure to MEDI-573 at the [REDACTED] level. In the event there is insufficient activity at the tissue level in the higher dose-expansion cohort, the sponsor may halt dose expansion and no additional subjects will be enrolled into the expansion phase.

Subject Evaluation/Follow-up

After informed consent has been obtained, screening evaluations will occur within 28 days prior to study entry and include the following evaluations: medical history; serum β human chorionic gonadotropin (β hCG) for women (unless surgically sterile or >1 year postmenopausal); complete physical examination (including height and weight); vital signs; electrocardiogram (ECG); routine laboratory evaluations (hematology, serum chemistry, and urinalysis); assessment of protocol-related adverse events (AEs) and serious adverse events (SAEs); notation of concomitant medications; and disease evaluations (including computed tomography [CT] or magnetic resonance imaging [MRI] scans, Karnofsky performance status [KPS]).

For subjects enrolled on the dose-escalation phase of the study, the following specimens will be collected:

- archived tumor biopsies (optional)
- biopsies obtained during procedures conducted in the course of routine patient care (optional)
- circulating tumor cells
- whole blood RNA

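### After Cycle 1, Section 4.7 items 5 and 6 and Table 3.5.5-1 give different stopping outcomes for some of the same subjects, and no precedence is stated

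*Protocol*

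**What the plan says.** **Section 4.7.** The lead-in is absolute: "An individual subject will not receive any further investigational product if any of the following occur in the subject in question". Item 5 lists "Occurrence of Grade 3 or Grade 4 hematologic or non-hematologic toxicity after the first cycle of treatment" and contains no condition on resolution, benefit or regulatory agreement. Item 6 lists toxicities of Grade 2 or higher, after Cycle 1, that have not recovered to Grade 1 or baseline within 7 days, unless clearly due to another cause. Item 6 names no cohorts; item 7, directly below it, does.

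**Section 3.5.5 and Table 3.5.5-1.** The table also governs the period after Cycle 1. It covers toxicities "that cannot be attributed to another cause such as disease progression or accident following the first cycle of treatment".

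- First Grade 3 or 4, Cohorts 1 to 5 and expansion: "Withhold MEDI-573 for up to 7 days until resolution to Grade ≤ 1 or baseline. Discontinue MEDI-573 if no clinical benefit has been documented". Dosing also ends if the toxicity is unresolved after more than 7 days of withholding, whatever the benefit.
- First Grade 3 or 4, Cohorts 6 and 7: "Discontinue MEDI-573 if no clinical benefit has been documented and the toxicity does not resolve to Grade ≤1 or baseline by Day 1" of the next cycle.
- All cohorts, if such a toxicity resolves and there is benefit: "the Food and Drug Administration (FDA) will be consulted regarding the possibility of continued administration of MEDI-573". Dosing should not go on unless the agency agrees.
- Second Grade 3 or 4: discontinue.
- Grade 2, Cohorts 6 and 7: "Discontinue MEDI-573 if the toxicity does not return to Grade ≤ 1 or baseline prior to Day 1 of the subsequent cycle", unless clearly due to another cause. In both schedule blocks, the Medical Monitor is consulted on whether dosing may continue for clinically insignificant Grade 2 laboratory events.

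**Section 2.4**, with matching text in the Study Abstract and Section 3.5.2: "Dose reduction for toxicities other than DLTs will be allowed as described in Section 3.5.5". The Abstract and Section 2.4 then refer to Section 4.7 for individual discontinuation, without ranking the two sections.

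**The concern.** A subject-level stopping rule should give one answer for one set of facts. Here two current sections cover the same period and can give two. If item 5 governs, the table's FDA route and its second-occurrence row could never operate, because no subject would still be on drug to reach them. If the table governs, a subject kept on drug has been dosed against Section 4.7.

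This is a first-in-human study whose first primary objective is safety and tolerability. Whether a subject stops for toxicity, and how many cycles that subject receives, would depend on which passage was followed. Stopping also changes the assessment schedule. On treatment, disease is assessed after every 2 cycles (6 weeks); after stopping for a reason other than progression or new anticancer therapy, it is assessed every 3 months. The dates that enter TTP and PFS can therefore shift for the same subject.

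**Working it through.** There is no sample-size or error-rate figure to reproduce. The check takes each case after Cycle 1 through both rule sets, limited to toxicities within the scope of both (no other clear cause).

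| Case | Section 4.7 | Table 3.5.5-1 | Agree? |
|---|---|---|---|
| 1. First Grade 3-4, Cohorts 1-5 or expansion, resolved within 7 days, benefit | Stop (item 5) | May continue with FDA agreement | No |
| 2. Same cohorts, no benefit | Stop | Stop | Yes |
| 3. Same cohorts, unresolved after 7 days | Stop | Stop | Yes |
| 4. First Grade 3-4, Cohorts 6-7, resolved by next Day 1, benefit | Stop (item 5) | May continue with FDA agreement | No |
| 5. First Grade 3-4, Cohorts 6-7, only one of benefit and resolution present | Stop (item 5) | Literal wording requires no stop | No |
| 6. Second Grade 3-4, any cohort | Stop | Stop | Yes |
| 7. Grade 2, Cohorts 6-7, lasting more than 7 days but resolved before next Day 1 | Stop (item 6) | No stop | No |

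**Cases 1 and 4** are the core conflict: resolution together with benefit.

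**Case 7, timing.** In Cohorts 6 and 7 a new cycle starts 21 days after the previous dose, so the next Day 1 is Day 22 (ignoring the +2-day visit window). A toxicity starting on Day d reaches item 6's limit at Day d + 7. Item 6 can stop a subject whom the table would not only if d + 7 < 22, that is, with onset before Day 15 (22 − 7 = 15). The Medical Monitor exception for insignificant laboratory findings adds a further difference, since item 6 has no counterpart to it.

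**Case 5** is a gap in the table as much as a conflict. The row requires a stop only when benefit and resolution are both absent. The FDA sentence covers only resolution together with benefit. Benefit with an unresolved toxicity is therefore not addressed by the table, although item 6 would stop that subject after 7 days. Resolution without benefit is not addressed either, and item 5 would stop that subject.

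**Dose-reduction cross-reference.** The Grade 2 entry for Cohorts 1 to 5 and expansion resumes treatment at an unchanged dose. The Grade 3 or 4 entries name no reduced dose. The text below the table mentions lowering later doses, but as a possible change to the escalation scheme after a safety review. No reduction rule for an individual subject is given.

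**Scale of one subject.** In an escalation cohort of 3 to 6, one subject is 1/3 = 33% or 1/6 = 17% of the cohort. In an expansion cohort of about 10, one subject is 1/10 = 10%. These figures show how much one discrepant case weighs; they do not predict how many will occur.

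**The case against.** The strongest reply is that the two sections seldom collide in practice and that the table mostly permits rather than orders dosing. Much of this stands.

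- A reader might infer that every subject with a first Grade 3 or 4 toxicity is affected. That is not so: in Cohorts 1 to 5 and expansion, both rules stop subjects without benefit and subjects unresolved after 7 days.
- A reader might infer that each site chooses the outcome. Continuing after a resolved Grade 3 or 4 toxicity needs FDA agreement, and insignificant Grade 2 laboratory events go to the Medical Monitor.
- A reader might infer that a site cannot comply with both sections. For a Grade 3 or 4 toxicity the table never orders continued dosing, so stopping under Section 4.7 breaches nothing in it. The fault is that the protocol does not settle whether continuation is allowed.
- A reader might take the conjunction in the Cohorts 6 and 7 row for a mistake. A different rule for a different schedule is not in itself an error; what can be said is that the row leaves combinations unaddressed.
- Item 5 is not absolute across Section 4.7, because item 2 exempts some infusion reactions up to Grade 3.
- The named primary summaries are AEs, SAEs and DLTs by cohort. Discontinuation rate and dose intensity are not named endpoints. Treatment-related AEs in the first 17 subjects were Grade 1 or 2.

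These points reduce the number of subjects. They do not remove cases 1, 4 and 7, where both sections are current text, neither is blacked out at the point in dispute, and neither is given precedence.

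**Conclusion.** An internal inconsistency that should be fixed. Of the seven cases compared, the rules agree in three and differ in four. The firm conflicts are a resolved first Grade 3 or 4 toxicity with benefit (all cohorts), and a Grade 2 toxicity in Cohorts 6 and 7 that outlasts 7 days but resolves before the next Day 1. The remaining Cohorts 6 and 7 case and the dose-reduction reference are drafting gaps.

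The number of subjects concerned is probably small; the protocol gives no rate from which to calculate it. For those subjects, treatment discontinuation, cycles received and the scan interval can differ. A reader might extend this to the MTD, but DLTs are counted only from Day 1 to Day 21 of Cycle 1, so DLT and MTD assessment is unaffected.

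The conclusion rests on the literal wording of the current body text and on the absence of any stated order between the sections. It takes no view on which clinical rule is right.

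**What to change.** The sponsor should:

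1. Reconcile Section 4.7 items 5 and 6 with Table 3.5.5-1, for the weekly and the every-3-week schedules, so that each case in the table above has one outcome. This includes the status of the FDA route, the second-occurrence row and the Medical Monitor exception.
2. Clarify the Cohorts 6 and 7 row for Grade 3 or 4 so that every combination of benefit and resolution is addressed.
3. In the Study Abstract and Sections 2.4 and 3.5.2, either delete the dose-reduction sentence or make it point to a rule that exists.

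The choice of clinical rule is the sponsor's. The cost is amendment wording, with no change to sample size, assessments or analysis. Until the text is amended, recording which rule was applied to each such event would let discontinuations be tabulated consistently.
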